## VERSION HISTORY

| Version                  | Date        | Protocol Update / Amendment |
|--------------------------|-------------|-----------------------------|
| Original Document
1.0 | 31 Mar 2022 | Not applicable              |
| 2.0                      | 15 Jul 2022 | Update                      |

### Name of Investigational Products:

THS Blade device  
THS Induction Mono device  
THS Induction Mid device  
Subjects' own cigarette brands

### Study Title:

A randomized, controlled, open-label, 4 parallel arms study to demonstrate reductions in exposure to selected harmful and potentially harmful constituents (HPHC) of cigarette (CIG) smoke in healthy smokers switching to different versions of Tobacco Heating System (THS) compared to continuing CIG smoking, for 5 days in confinement

### Study Number:

P1-REXC-10

### Short Title:

Reduced exposure to HPHC in smokers switching from cigarettes to different versions of THS

### Primary Objective and Endpoints:

The primary objective is the joint evaluation of the following hypotheses:

1. To demonstrate the reduction of biomarkers of exposure (BoExp) to selected harmful and potentially harmful constituents (HPHC) detailed in [Table 1](#) in smokers switching from CIG to THS Blade device compared to continuing CIG smoking for 5 days.
2. And to demonstrate the reduction of BoExp to selected HPHC detailed in [Table 1](#) in smokers switching from CIG to THS Induction Mono device compared to continuing CIG smoking for 5 days.

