### 12.5.1.5 Success Criteria

The primary study hypothesis is about demonstrating the reduction of the five BoExp to selected HPHC listed in [Table 3](#) in smokers switching from CIG to each of the THS variants (THS Blade device, or THS Induction Mono device, or THS Induction Mid device, respectively) for 5 days as compared to those who continue smoking CIG. For each individual BoExp, this will be evaluated using the 1-sided statistical test with a type I error level of 2.5% given by the ‘lsmestimate’ statement ‘Contrast every THS arms (THS Blade device, THS Induction Mono device or THS Induction Mid device) vs. CIG’ of the model described in section [12.5.1.4](#).

The study will be declared successful if all ratios of the geometric means between every THS arms (THS Blade device, THS Induction Mono device or THS Induction Mid Device) over CIG is statistically lower than 1 at Day 5 for all five BoExp tested in the primary objective given in [Table 3](#).

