## 12.6 Secondary Objectives

### 12.6.1 Key Secondary Objectives

[figure not shown]
The key secondary objectives are to demonstrate the reduction of additional BoExp to selected HPHC given in Table 4 in smokers who switch from CIGs to THS use compared to those who continue to smoke CIG. The statistical analysis for each of these additional BoExp for each THS arm (THS Blade device, THS Induction Mono device or THS Induction Mid device) will be done similarly to those belonging to the primary objective (except the Success Criteria described in section 12.5.1.5). More specifically, the analyses described as primary estimand (see section 12.5.1.4) can be repeated, replacing the endpoints listed in Table 3 by those of Table 4 and performing the analysis by THS arm sequentially.

The evaluation of the key secondary objectives will be done using a procedure of fixed sequence testing (see Figure 3). This first key secondary objective related to the THS Blade device will only be tested if the primary objective is demonstrated for all THS arms. This fixed sequence of study hypotheses ensures that the overall study-wise risk of type I error is preserved at the 2.5% (see section 12.9.3).

If both the primary and first key secondary objectives are declared successful, then the 2nd key secondary objective will be tested with type I error level of 2.5%, this time using the contrast THS Induction Mono device vs. CIG and the BoExp listed in Table 4. If this 2nd key secondary objective is also declared successful, then the 3rd key secondary objective can be tested similarly, this time with the BoExp listed in Table 4 for the THS Induction Mid device arm. If, along the procedure from the primary objective up to the 3rd key secondary objective, any of the objectives are not declared successful, the sequence testing will stop, and further testing will not be permitted.

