### 12.9.3 Study Significance Level

In this study, the overall familywise type I error will be preserved at the  $\alpha$ -level of 2.5% (1-sided tests will be conducted for the primary and key secondary study hypotheses). This will be done by using a fixed sequence of testing:

- primary objective, then if significant
- 1st key secondary objective, then if significant
- 2nd key secondary objective, then if significant
- 3rd key secondary objective

All objectives will be tested at the 2.5% type I error level until one of the objectives is rejected and no further testing will be performed (in this case, only subsequent exploratory testing will be conducted).

The primary study hypothesis (as assessed using the primary estimand defined in section 12.5.1) will be tested one-sided with a type I error  $\alpha$ -level of 2.5%. The associated 1-sided 97.5% confidence interval will be provided. This will be applied to all BoExp of Table 3 that are part of the primary study hypothesis (every BoExp for each THS arms need to pass for the objective to be considered demonstrated).

If the primary study hypothesis is demonstrated, the same  $\alpha$ -level of 2.5% will be used for the 1st key secondary hypothesis and the associated 1-sided 97.5% confidence interval will be provided. This will be applied to all BoExp of Table 4 that are part of the 1st key secondary study hypothesis (all need to pass for the THS Blade device arm versus CIG for the 1st key secondary objective to be successful).

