### Confidentiality Statement

Data and information contained in this document are considered to constitute trade secrets and confidential commercial information, and the legal protections provided to such trade secrets and confidential information are hereby claimed under the provisions of applicable law. No part of this document may be publicly disclosed without the written consent of Philip Morris Products S.A.

If the primary study hypothesis is not demonstrated, the 1st key secondary hypothesis (and all subsequent key secondary objectives) will be considered exploratory and conducted 2-sided at the  $\alpha$ -level of 5% and the associated 2-sided 95% confidence interval will be provided.

The analysis will proceed in a similar way for the following key secondary objectives.

For all the exploratory objectives, the statistical tests will be considered exploratory, 2-sided, and conducted at the  $\alpha$ -level of 5%. Associated 2-sided 95% confidence intervals will be provided.

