3.5.2 Evaluation Criteria

The study will be declared successful if a reduction is demonstrated for each and every endpoint tested to support the set of primary objectives (3-HPMA, 2-CyEMA, MHBMA, total NNAL, and COHb), using a one-sided test-wise type I error level of 2.5%.

Confidentiality Statement

Data and information contained in this document are considered to constitute trade secrets and confidential commercial information, and the legal protections provided to such trade secrets and confidential information are hereby claimed under the provisions of applicable law. No part of this document may be publicly disclosed without the written consent of Philip Morris Products S.A.

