9.6.3.1 Key Secondary Objectives

The key secondary objectives are to demonstrate the reduction of additional BoExp to selected HPHC given in [Table 2](#) in smokers who switch from CIGs to THS use compared to those who continue to smoke CIG. The statistical analysis for each of these additional BoExp for each THS arm (THS Blade device, THS Induction Mono device or THS Induction Mid device) will be done similarly to those belonging to the primary objective (except the Success Criteria). More specifically, the analyses described as primary estimand (see section [9.6.1.2](#)) can be repeated, replacing the endpoints listed in [Table 1](#) by those of [Table 2](#) and performing the analysis by THS arm sequentially.

The evaluation of the key secondary objectives will be done using a procedure of fixed sequence testing (see [Figure 2](#)). This first key secondary objective related to the THS Blade device will only be tested if the primary objective is demonstrated for all THS arms. This fixed sequence of study hypotheses ensures that the overall study-wise risk of type I error is preserved at the 2.5%.

If both the primary and first key secondary objectives are declared successful, then the 2nd key secondary objective will be tested with type I error level of 2.5%, this time using the contrast THS Induction Mono device vs. CIG and the BoExp listed in [Table 2](#). If this 2nd key secondary objective is also declared successful, then the 3rd key secondary objective can be tested similarly for the THS Induction Mid device arm. If, along the procedure from the primary objective up to the 3rd key secondary objective, any of the objectives are not declared successful, the sequence testing will stop, and further testing will not be permitted.

Figure 2. Representation of the Procedure of Fixed Sequence Testing

Confidentiality Statement

Data and information contained in this document are considered to constitute trade secrets and confidential commercial information, and the legal protections provided to such trade secrets and confidential information are hereby claimed under the provisions of applicable law. No part of this document may be publicly disclosed without the written consent of Philip Morris Products S.A.

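### The all-or-nothing primary rule across three devices is valid, but a Blade, Mono, Mid fixed sequence at the same one-sided 2.5% would add confirmed claims for devices tested ahead of a failing one

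*Protocol*

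**What the plan says.** Protocol 3.1 and the synopsis list three device hypotheses (Blade, Induction Mono, Induction Mid) under one heading: "The primary objective is the joint evaluation of the following hypotheses". Protocol 12.5.1.5 makes success depend on every device-to-cigarette ratio being below 1 at Day 5 for all five biomarkers. Protocol 12.9.3 repeats that "every BoExp for each THS arms need to pass for the objective to be considered demonstrated". SAP 3.5.1 writes the primary hypothesis H1 as 15 ratios joined by 'and', and SAP 3.5.2 adds: "The study will be declared successful if a reduction is demonstrated for each and every endpoint tested to support the set of primary objectives".

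The same all-device condition controls the next step. In Protocol 12.6.1 the first key secondary objective "will only be tested if the primary objective is demonstrated for all THS arms". If the primary fails, Protocol 12.9.3 says the first key secondary hypothesis "and all subsequent key secondary objectives) will be considered exploratory and conducted 2-sided at the" 5% level.

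The key secondary objectives, by contrast, go device by device. After Blade and Mono, SAP 9.6.3.1 continues: "If this 2nd key secondary objective is also declared successful, then the 3rd key secondary objective can be tested similarly for the THS Induction Mid" arm. The stated purpose of the sequence is that "the overall familywise type I error will be preserved at the" 2.5% level.

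For the primary biomarkers, the single-device comparisons with cigarettes are supplementary, with unadjusted p-values (Protocol 12.5.1.6, SAP 9.6.1.3). The test named for the primary hypothesis is one contrast of the three THS arms jointly against cigarettes, with its syntax left open (Protocol 12.5.1.4, SAP 9.6.1.2).

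**The concern.** The three devices are separate products with separately numbered hypotheses. Under the written success rule, the chance of a confirmed statement about Blade equals the chance that all three devices pass on all five biomarkers. If Mid misses on one biomarker, Blade and Mono lose confirmatory status even if each passes all five, and no key secondary objective can be tested confirmatorily.

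Protocol 2.1.2 describes the Induction devices as newer versions whose reduction is still to be demonstrated. The power inputs in Protocol 12.9.4 come from earlier tobacco heating system studies, with a similar effect expected here. The claim for any one device thus depends on that expectation holding for all three. The plan already uses a device-ordered sequence for the key secondaries, so a less fragile structure is at hand.

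**Working it through.** **Inputs.** 20 randomized per arm and 15% missing, so 17 evaluable (20 × 0.85). One-sided two-sample t-test on the log scale at 2.5% (Protocol 12.9.4). Geometric mean ratios (GMR) and geometric coefficients of variation (GCV) are from Protocol Table 13. Log-scale SD = √ln(1 + GCV²), reading GCV as between-subject.

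**The plan's own figure.** 0.99³ = 97.03%, which reproduces the stated 97% for three devices. Direct t-test calculation for 3 devices × 5 biomarkers gives 99.7% to above 99.9% at 20 per arm, and 98.7% to above 99.9% at 17 per arm, over the four source studies. The plan's figure is therefore a floor.

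**Why the sequence dominates.** Let A, B and C be the events that Blade, Mono and Mid each pass all five tests at 2.5%.
- The joint rule claims all three devices on A∩B∩C and otherwise claims nothing.
- The sequence claims Blade on A, Blade and Mono on A∩B, and all three on A∩B∩C. The last event is identical to the joint rule's.
- Error control: take the first device in the order for which at least one ratio is truly not below 1. A false claim requires that device to pass all five tests, including the one whose null is true, so its probability is at most 2.5%.
- Simulation check (400,000 runs, shared cigarette arm, 17 per arm, one biomarker per device, five null patterns): family-wise error was 2.43% to 2.53%.

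**Size on the plan's 99% per device (independent devices).**
- No confirmed claim, joint rule: 1 − 0.99³ = 2.97%.
- No confirmed claim, sequence: 1 − 0.99 = 1.00%.
- Exactly one device fails: 3 × 0.99² × 0.01 = 2.94%. In one third of these (0.98%) the failing device is Blade and the sequence saves nothing.

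**Size on the least favourable source study (NCT01970982), 17 per arm.**
- 3-HPMA: SD = √ln(1 + 0.3957²) = 0.381, ln(0.5286) = −0.638, SE = 0.381 × √(2/17) = 0.131, power 99.71%.
- Total NNAL: SD 0.408, ln(0.4903) = −0.713, SE 0.140, power 99.86%.
- The other three biomarkers are at practically 100%.
- Per device: 0.9971 × 0.9986 = 99.57%. Three devices if independent: 0.9957³ = 98.7%.
- With the shared cigarette arm simulated (five biomarkers independent): Blade 99.5% to 99.6%, Blade and Mono 99.1% to 99.2%, all three 98.8%. No confirmed claim: about 1.2% under the joint rule, about 0.5% under the sequence.

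**If Mid does worse than assumed.** The Mid ratios below are assumptions; Blade and Mono stay at the NCT01970982 values.

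| Assumed Mid ratio | All three pass, 17 per arm | All three pass, 20 per arm | Blade and Mono pass |
|---|---|---|---|
| COHb 0.85 | 81% | 87% | about 99% or more |
| COHb 0.90 | 46% | 53% | about 99% or more |
| 3-HPMA 0.80 | about 38% | 44% | about 99% or more |

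Analytic check at 17 per arm for COHb 0.85: SD 0.160, SE 0.055, ln(0.85) = −0.163, single-test power 82.0%; × 0.99 for Blade and Mono ≈ 81%.

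For a uniform shortfall to 90% power per device, the joint rule confirms anything in 0.9³ = 72.9% of trials, against 90% for Blade under the sequence.

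**The named contrast.** All of the above applies the written each-device rule. If the joint contrast were coded as the average of the three THS arms, a device with no effect on 3-HPMA would usually not fail that test. With the other two devices at 52.86%, the averaged ratio is 0.5286^(2/3) = 0.654 and power is 97.5% (17 per arm) or 98.9% (20 per arm). That coding would not enforce the success rule.

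**The case against.** **The joint rule is deliberate and valid.** Requiring every component to pass needs no alpha adjustment, and it suits the aim in Protocol 2.1.2 of showing comparable reductions across versions. This stands. A reader might infer that the rule is an error or inflates type I error; nothing in the documents supports that.

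**The sequence does not in general keep the other two devices.** That stronger reading is tempting, but it holds only when Mid alone fails. Protocol 2.1.2 also says Blade already has an FDA exposure modification authorization, so the first step protects the device that arguably needs a claim least, and a Blade miss still loses both newer ones. This stands as a limit on the benefit. Another prespecified order would hold the error rate equally well. Protecting the other two whichever device fails needs an alpha split: at 2.5%/3 = 0.83%, power per device in the least favourable study is 98.1% (17 per arm) or 99.5% (20 per arm).

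**The large losses rest on assumed Mid ratios.** Table 13 gives COHb ratios of 0.23 to 0.47 and 3-HPMA ratios of 0.42 to 0.53. Mono and Mid use the same Induction sticks, and similar effects are expected. The documents give no reason to expect Mid alone to reach 0.80 to 0.90, so those rows show sensitivity and are not a forecast.

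**No evidence is lost.** Device-level ratios, intervals and p-values are reported for Days 1 to 5 whatever happens. This is right: only confirmatory status is lost.

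**The order is fixed only for the key secondaries.** Also right. Extending it to the primary is a change to the hypothesis and needs an amendment. None of these points disputes that the sequence can only add confirmed claims.

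**Conclusion.** The point holds as an avoidable cost in a valid design. Under the written success rule, any single miss among 15 comparisons removes every confirmatory claim. A device-level sequence at the same one-sided 2.5% leaves study success unchanged and keeps the claims for devices ahead of the failing one.

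On the plan's inputs the gain is at most about 2 percentage points in the chance of at least one confirmed claim, and under 1 point in the least favourable source study. It becomes large only if a later device falls well short of Table 13. A reader might infer that the trial is underpowered or likely to end without a claim; the plan's figures support neither.

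These sizes assume that the GCVs are between-subject on the log scale, that the five biomarkers are independent, and that each device is tested against cigarettes separately. The last assumption is not secured by the plan as written, because the named joint contrast does not clearly carry out the each-device rule. Reconciling the two is the first step.

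**What to change.** In Protocol 12.5.1.5, 12.6.1, 12.9.3 and Figure 3, and in SAP 3.5.1, 9.1.7, 9.6.1.2 and Figure 2:

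- Split the primary hypothesis into H1a (Blade, all five biomarkers), H1b (Induction Mono) and H1c (Induction Mid).
- Test them in that order at one-sided 2.5%, each only if the previous one is demonstrated, using that device's own Day 5 contrast with cigarettes.
- Keep study success as all three demonstrated, and start the key secondary sequence after H1c as now.
- State that H1a, or H1a and H1b, remain confirmatory if a later step fails.
- In Protocol 12.5.1.4 and 12.5.1.6 and SAP 9.6.1.2 and 9.6.1.3, replace the joint THS contrast as the primary test with the device contrasts, or define it so that it agrees with them.
- While editing SAP 9.1.7, correct the gate, which lets testing proceed when a hypothesis is not rejected, and remove the undefined fourth key secondary objective.

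The cost is a protocol amendment and a SAP revision of wording and two figures. Sample size, alpha, data collection and the mixed model do not change. The change must be in place before biomarker data are unblinded, which the blinding tables in both documents tie to SAP finalization.

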### Confidentiality Statement

Data and information contained in this document are considered to constitute trade secrets and confidential commercial information, and the legal protections provided to such trade secrets and confidential information are hereby claimed under the provisions of applicable law. No part of this document may be publicly disclosed without the written consent of Philip Morris Products S.A.

3. And to demonstrate the reduction of BoExp to selected HPHC detailed in [Table 1](#) in smokers switching from CIG to THS Induction Mid device compared to continuing CIG smoking for 5 days.

**Table 1 List of BoExp Used in the Primary Objective**

| BoExp   | HPHC                                   | Matrix             |
|---|--|--------------------|
| 3-hydroxypropyl mercapturic acid ( 3-HPMA )                                    | Acrolein                               | Urine  |
| 2-cyanoethyl mercapturic acid N-acetyl-S-(2-cyanoethyl)-L-cysteine ( 2-CyEMA ) | Acrylonitrile                          | Urine  |
| Monohydroxybutenyl mercapturic acid ( MHBMA )                                  | 1,3-butadiene                          | Urine  |
| Total 4-(methylnitrosamino)-1-(3-pyridyl)-1-butanol ( total NNAL )             | 4-(methylnitrosamino)-1-(3-pyridyl)-1- | Urine  |
| Carboxyhemoglobin ( COHb )   | Carbon monoxide (CO)                   | Blood  |

BoExp in urine will be expressed as concentration adjusted for creatinine in 24-hour urine;

BoExp in blood expressed as % of saturation of hemoglobin.

**Secondary Objectives and Endpoints:**

**Key secondary objectives**

1. To demonstrate the reduction of BoExp to selected HPHC detailed in [Table 2](#) in smokers switching from CIG to THS Blade device compared to continuing CIG smoking for 5 days.
2. To demonstrate the reduction of BoExp to selected HPHC detailed in [Table 2](#) in smokers switching from CIG to THS Induction Mono device compared to continuing CIG smoking for 5 days.
3. To demonstrate the reduction of BoExp to selected HPHC detailed in [Table 2](#) in smokers switching from CIG to Induction Mid device compared to continuing CIG smoking for 5 days.

**Table 2 List of BoExp Used in the Key Secondary Objective**

| BoExp  | HPHC           | Matrix             |
|--|----------------|--------------------|
| S-phenylmercapturic acid ( S-PMA )        | Benzene        | Urine  |
| 2-hydroxyethylmercapturic acid ( 2-HEMA ) | Ethylene oxide | Urine  |

**Confidentiality Statement**

Data and information contained in this document are considered to constitute trade secrets and confidential commercial information, and the legal protections provided to such trade secrets and confidential information are hereby claimed under the provisions of applicable law. No part of this document may be publicly disclosed without the written consent of Philip Morris Products S.A.

|   |                      |                    |
|---|----------------------|--------------------|
| 3-hydroxy-1-methylpropylmercapturic acid ( 3-HMPMA ) | Crotonaldehyde       | Urine  |
| Total N-nitrosonornicotine ( total NNN )             | N-nitrosonornicotine | Urine  |
| Total 3-hydroxybenzo(a)pyrene ( 3-OH-B[a]P )         | Benzo(a)pyrene       | Urine  |
| 4-aminobiphenyl ( 4-ABP )                            | 4-aminobiphenyl      | Urine  |
| 2-aminonaphthalene ( 2-NA )                          | 2-aminonaphthalene   | Urine  |

BoExp in urine expressed as concentration adjusted for creatinine in 24-hour urine

### Other Secondary objective

1. To monitor the safety profile during the study.

#### Endpoints

- Incidents of adverse events (AEs) and serious adverse events (SAEs)
- Incidence of Device malfunction and product complaints (e.g., events related to charger, holder, or sticks)
- Vital sign changes from baseline (systolic and diastolic blood pressure, heart rate and respiratory rate)
- Laboratory safety panel changes from baseline
- Concomitant medication (ConMed)
- Electrocardiogram (ECG) changes from baseline (heart rate, PR, QRS, QT and QTcF intervals)
- Spirometry changes from baseline (forced expiratory volume in 1 second [FEV1], FEV1 % predicted, forced vital capacity [FVC]), FVC % predicted, FEV1/FVC)

